# Cooking for Health Optimization with Patients (CHOP) Protocol

#### 1. Study aim, background, and design

There is a global nutrition-related chronic disease epidemic. The research supports how nutrition education classes with hands-on cooking can be a very effective way to improve people's health individually and in families. But there are not many studies that say what is the best combination of nutrition educating and cooking classes, or who to show such classes work with patients and with medical professionals like doctors.

Tulane University has a pioneering medical school-based teaching kitchen, The Goldring Center for Culinary Medicine (GCCM), that wants to know what is best type of such classes to teach medical professionals and trainees how to counsel patients on nutrition, and the best classes to teach patients how to improve their health while still eating the meals they enjoy individually and with their families. To do this, GCCM will lead the research study, Cooking for Health Optimization with Patients (CHOP), as the world's first and largest study of its kind to compare effectiveness of hands-on cooking and nutrition education classes to the standard of nutrition education care. This will help answer how teaching medical professionals how to educate patients about nutrition impact their dietary habits and attitudes and competencies (DACs) educating patients, and how their DACs impact their patients' health, in addition to how classes for non-medical professionals directly improves their health.

CHOP is a prospective observational cohort study with four tracks ([1] medical professionals, [2] community, [3] employee, and [4] randomized controlled trial [RCT]) to allow results to be compared among the subjects in the four tracks. [1] Current and future medical professionals will be trained in classes within their track in how to educate patients about nutrition, and their results for their DACs will be compared to those who receive traditional clinical education. [2] Adults, adolescents, and children 7 years and older will be offered classes in their community track to allow comparison of their DACs and health metrics with those who do not take the classes. [3] Employees and their families who take the GCCM classes as employee wellness programing will have their DAC and health metrics compared to employees who do not take the classes. And finally, [4] subjects with such chronic health conditions as diabetes will be randomized with equal 50% chance to either taking the GCCM classes or receiving medical nutrition therapy (MNT) with a registered dietician (RD).

DAC surveys will take place for the first track at the beginning and end of each academic year. Surveys will take place for the last three tracks at the first and last class for the treatment (GCCM) class group, and the beginning of the study and 2-3 months later for the control groups (those who do not take the classes). The same adult and children surveys will be used across tracks [2]-[4] for adults 18 years and older and children 7-17 respectively. Medical professionals in [1] will have the same survey.

CHOP unites such analyses as diffusion of innovation (DOI), social network, and simulation-based medical education with deliberate practice (SBME-DP) along with rigorous statistical methods to answer these questions and hopefully benefit society. Results will be strengthened by using self regulation survey with Tulane marketing students to better design the DAC survey based on understanding what DACs predict

Version Date: 09/26/15 Version Number: 1 Page 2 of 9 certain nutrition behavior, in addition to comparison to the de-identified National Health and Nutrition Examination Survey (NHANES) for national trends in diet and similar health metrics and behaviors.

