# 2. Subject Population

[1] Medical professionals track: All participants (over 17) who have matriculated to the Tulane University Health Sciences Center as students or residents in addition to physicians participating in the curriculum as continuing medical education (CME) credits for a target sample of 10,000 respondents. Subjects will be offered the survey from medical school through residency and into medical practice. Up to 1,000 marketing students will be offered a self-regulation survey.

[2] Community track: Adults 17 years and older and children 7-17 in the Greater New Orleans area for a target sample of 6,000 subjects (3,000 taking the classes and the rest not). Subjects will be followed for three years after their class participation or lack thereof based upon standards for such studies.

[3] Employee track: Employees and their family members 7 years and older affiliated with Laitram, LLC for a target sample of 3,000 subjects (1,500 taking the classes and the rest not). Subjects will be followed for three years after their class participation or lack thereof based upon standards for such studies.

[4] RCT track: Adults 17 years and older with diagnosed diabetes, hypertension, hyperlipidemia, cardiovascular disease, or past history of cerebrovascular disease or their pre-diagnosis conditions (i.e. pre-diabetes as the condition at risk for developing diabetes) for a target sample of 500 subjects. Subjects will be followed for three years after their class participation or lack thereof based upon standards for such studies.

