# 3. Procedure

[1] Medical professionals track: An internet link will be distributed to subjects through the list-serves for each class at the beginning and end of each academic year after they have had the opportunity to participate or not in the voluntary GCCM classes. Residents and practicing physicians who identify themselves through the GCCM website will be subsequently offered the survey. Marketing students will be offered an online survey about self-regulation and nutrition through their marketing class to improve the medical professionals survey.

[2] Community, [3] Employee, and [4] RCT tracks: Subjects in the treatment group will receive up to 20 evidence-based classes (50 hours) of cooking and nutrition education that cover the Mediterranean diet, food shopping, cooking, and storage. Subjects in the control groups for [2] and [3] will not receive the classes, and control subjects in [4] will receive MNT. Control subjects in [2] will additionally have the opportunity to receive either healthy food vouchers for 2 months or have nutrition education for their children before they enroll in the classes in order to compare if increased healthy food access and education compared to GCCM classes best prepares them to benefit from nutrition education. DAC surveys will be used at the beginning and end of the classes for the treatment group, and beginning of the study and 2-3 months later for the control group. Health metrics will be assessed from health records for subjects retrospectively 3 years before and 3 years after their treatment or control exposure, once subjects provide release to the study team of their records with appropriate safeguards to protect

Version Date: 09/26/15 Version Number: 1 Page 3 of 9 the safety of their data. Recruitment for [2] will be through GCCM's website, [3] will be through Laitram that promotes the classes to their employees, and [4] through Tulane University Hospital and Clinic (including the Internal Medicine Practice, Uptown Square clinic, Endocrinology clinic, and Metairie Multispecialty clinic) by study staff. Health metrics will be obtained for [2,4] from Tulane University Hospital and Clinic if subjects' information is stored there, from Marathon Health the third party provider of health care for [3], and from non-Tulane health care institutions for [2,4]. Marathon and non-Tulane facility health information release forms will be provided to subjects as needed at the time of informed consent.

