# 4. Risks

There are no foreseeable risks. However, if subjects feel at all uncomfortable, they may cease participation at any time and forgo participation. Subjects' names will not appear anywhere on the surveys, but stored rather than dummy IDs that subjects generate themselves. Survey data for tracks [1-4] and health metric data will for tracks [2-4] will be stored on an encrypted computer owned by Tulane University using files that will be password protected. Electronic backup will be made to a secure shared drive hosted by Tulane University Information Technology Services. Only study staff will have direct access to the data. Only study staff will have access to the code key that identifies participants. This will be stored on a separate dataset on a secure, password protected Tulane hard drive. Subject survey responses are also protected by being collected through Qualtrics, an advanced online survey system used by research teams. Servers are protected by high-end firewall systems, and scans are performed regularly to ensure that any vulnerabilities are quickly found and patched. Complete penetration tests are performed yearly. All services have quick failover points and redundant hardware, with complete backups performed nightly. The confidential system component design uses multiple checks to certify that packets from one subsystem can only be received by a designated subsystem. Access to systems is severely restricted to specific individuals, whose access is monitored and audited for compliance. Customer data are stored in a specific location; it does not float around in the "cloud." In addition, all data are processed in that location, and are not moved to another jurisdictional area. In other words, if data are collected in the U.S., all data are processed in the U.S. Qualtrics uses Transport Layer Security (TLS) encryption (also known as HTTPS) for all transmitted data. Qualtrics also protects surveys with passwords and HTTP referrer checking. Qualtrics services are hosted by trusted data centers that are independently audited using the industry standard SSAE-16 method. Qualtrics deploys the general requirements set forth by many Federal Acts, including the FISMA Act of 2002. They meet or exceed the minimum requirements as outlined in FIPS Publication 200. Qualtrics safeguards all responder data, and uses secure data centers to ensure the highest protection as per requirements of HITECH (Health Information Technology for Economic and Clinical Health Act) to ensure that data are properly protected and best security practices followed. In the case of an emergency for the treatment group (though not expected), please exit GCCM through the labeled exits and follow the instructions of the class facilitators familiar with the facility.

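### The class group's second DAC survey depends on staying to the end of the classes, the controls' survey does not, and class-takers who stop have no planned follow-up

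*Combined protocol and SAP*

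**What the plan says.** Section 1 of the protocol sets the survey schedule for tracks 2 to 4 (community, employee, randomised): "Surveys will take place for the last three tracks at the first and last class for the treatment (GCCM) class group". Section 3 repeats it in slightly different words: "DAC surveys will be used at the beginning and end of the classes for the treatment group". For controls, Section 3 gives "beginning of the study and 2-3 months later for the control group", which is a calendar rule with no attendance condition.

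The exposure may be long: "Subjects in the treatment group will receive up to 20 evidence-based classes (50 hours) of cooking and nutrition education". No minimum attendance, class frequency or end date is given. Section 4 lets subjects who feel uncomfortable stop: "they may cease participation at any time and forgo participation". That right covers controls as well as class-takers.

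Neither the protocol nor the SAP describes a second survey for class-takers who stop, an expected dropout or response rate, an analysis set for tracks 2 to 4, or a method for missing surveys. The SAP (Machine Learning and Statistical Analysis) lists a propensity score for receiving the classes, regression covariates suited to medical trainees, and fixed effects described as making each subject his or her own control.

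**The concern.** A class-taker who stops attending has a first survey and, under the stated schedule, no second one. Someone who attends once has a first and last class on the same visit. A control needs no attendance to be surveyed again. The two groups are therefore filtered differently before any DAC comparison is made.

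If staying in the course is related to how DAC answers move, for example because people leave when the classes are not helping them, the class group's measured change is too favourable. The propensity score does not address this because it models who receives the classes, not who finishes them. The fixed effects do not address it either, because a person with only a first survey adds nothing to a within-person contrast. The large targets (3,000 per group in the community track, 1,500 in the employee track) shrink random error but leave this bias in place, so even a small one could be declared significant. At stake is the DAC comparison, for which the SAP's methods claim causal inference.

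**Working it through.** The plan gives no attrition or response figure to reproduce, and its sample-size figure of 263 cases does not enter this point. What follows illustrates size under stated assumptions.

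**Inputs from the documents.** Community track 3,000 per group and employee track 1,500 per group (Section 2); two-sided 5% test (SAP).

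**Assumed.** No true class effect; 50% favourable rate on a binary DAC item; 30% of class-takers without a second survey; correlation r between latent persistence and the latent outcome of 0.2 (range 0.1 to 0.3).

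**Step 1. Follow-up answers only, every control scored.** Class-takers are scored if their persistence score exceeds its 30th percentile. With bivariate normal scores and r = 0.2, the favourable rate among those scored is 0.540. Those not scored then have (0.500 − 0.7 × 0.540)/0.3 = 0.407, so the assumption amounts to a gap of about 13 points.
- OR = (0.540/0.460)/(0.5/0.5) = 1.17; ln OR = 0.160.
- SE = √[1/(2,100 × 0.540 × 0.460) + 1/(3,000 × 0.25)] = √(0.00192 + 0.00133) = 0.057.
- 0.160/0.057 = 2.80, so the two-sided 5% test rejects about 80% of the time.

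| r | Apparent OR | Community (2,100 v 3,000) | Employee (1,050 v 1,500) |
|---|---|---|---|
| 0.1 | 1.08 | 29% | 17% |
| 0.2 | 1.17 | 80% | 51% |
| 0.3 | 1.27 | 99% | 85% |

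With only 10% lost and r = 0.1, the OR is 1.03 and the community rate 9%. With r = 0 there is no bias.

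**Step 2. The same comparison when controls are also lost** (community track, r = 0.2, same selection in both groups, 30% class-group loss).
- 20% control loss: the controls' rate rises to 0.528, so OR = 1.173/(0.528/0.472) = 1.05; false positives about 13%.
- 30% control loss: OR 1.00, no bias.
- 40% control loss: OR 0.95; the direction reverses.

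**Step 3. Within-person comparison using the baseline survey** (community track, 30% class-group loss, no control loss, r = 0.2).
- If persistence depends only on a stable trait, conditional logistic regression gives OR 1.00 and about 5% false positives.
- If persistence depends on DAC change, a false effect remains: about 70% false positives in one simulation of a binary item. This figure depends on how stable each person's answers are assumed to be.
- For a continuous change score, the expected bias is r·φ(z)/(1 − d), where d is the fraction lost and z its normal quantile: 0.2 × 0.348/0.7 = 0.10 SD. Simulated false positives were 93% in the community track and 71% in the employee track. If controls also lose 10% with the same r, the bias falls to 0.06 SD and the community rate to 57%.

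**Step 4. Everyone who starts is surveyed.** With 30% stopping and r = 0.3, but all of them answering, the simulated null difference is 0.00 SD, with false-positive rates of 5.1% (3,000 per group) and 4.3% (1,500 per group).

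**The case against.** The strongest reply is that the SAP already aims at this. People who persist may be more motivated, healthier or better off, but those are largely stable traits. Both groups have a baseline survey, and a within-person analysis removes stable traits; Step 3 confirms it. This stands, and it narrows the point to selection related to DAC change. It is not full reassurance: the SAP is written around medical trainees, and its model equation does not clearly show subject-level effects, so it is not certain that tracks 2 to 4 would be analysed within person.

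A reader might infer that every control will be scored and that the error rate is therefore about 80%. The documents do not support that. Controls must answer a second survey, unpaid and without class contact, and no response rate is given. Step 2 shows that the bias can shrink, vanish or reverse.

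A reader might also infer that class-takers who stop cannot be scored at all. That is too strong. The survey is online (Sections 4 and 12), and the wording in Section 3 about the end of the classes need not require attendance. The gap is in the planned schedule; follow-up is technically possible. Reading the last class as each person's own last attended class does not close it, since staff usually cannot know that a visit will be the last.

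Finally, in the self-selected tracks, analysing starters or completers is partly a choice of estimand. That is fair, but the plan does not state the choice.

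**Conclusion.** The point holds as a gap in the design of the DAC follow-up in tracks 2 to 4. Following the stated schedule measures the class group's DAC change mainly in people who persist, while controls face no attendance condition, and nothing in the SAP models completion.

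A false class effect is possible but not established. It requires persistence to be related to DAC change, or an analysis that does not use the baseline survey, together with losses that differ between groups. The documents give neither the dropout, nor the control non-response, nor the strength of that link. The plausible range therefore runs from no bias, through OR 1.05 to 1.17 on follow-up answers under the central assumptions, to a slight reversal if controls are lost more often. The 80% figure should not be read as the trial's error rate.

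The health-record outcomes, taken over three years before and after exposure, do not depend on attending the last class and are unaffected.

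**What to change.** In Sections 1 and 3, send the second DAC survey through the existing online link to every subject who started the classes, attending or not, at the scheduled end date of that subject's class series. Time the matched controls' second survey to the same interval from the first. Tying class-takers to the present control window of 2 to 3 months would be less safe: no class frequency is given, so the survey could fall mid-course.

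In the SAP, make all starters, with the baseline survey used, the main DAC comparison. Report last-class completers as a secondary analysis, and report second-survey response rates by group. Apply the same survey rule to the randomised track, which the same sentence governs.

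The cost is a sentence or two in each section, some reminder work, and possibly a line in the consent text, because Section 10 says telephone numbers are collected for class reminders. The estimated effect will probably be somewhat smaller because partial attenders are included. People who withdraw from the research itself will still be missing.

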#### 10. Consent process and documentation

[1] Medical professionals track: A waiver of documentation of consent has been attached to this package for both medical professionals and trainees and marketing students, due to the information necessary for informed consent being provided in the recruitment email and the significant logistical challenges of documenting consent individually for such a large number of respondents remotely accessing the survey through the confidential online survey link. Email addresses are collected to verify the accuracy of the self-generated dummy IDs for subjects who respond to repeat surveys, and then the emails are deleted from the dataset used for longitudinal analysis.

[2] Community, [3] Employee, and [4] RCT tracks: A full description of the research will be discussed with subjects regarding both study groups. Discussion about the risks and benefits will be undertaken with prospective participants. This will mirror the written information in the consent form. After full information is discussed and questions are answered the participants the consent form will be reviewed and subjects will be asked to sign the form if they are interested in being involved (adults) or assent (children). Telephone numbers are collected based on GCCM experience over the past four years that class participants find reminders about classes helpful.

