# 12. Survey links

[1] CHOP-Medical Professionals: http://tulane.qualtrics.com/SE/?SID=SV\_57Pu9twXUczA4gR.
[2-4] CHOP-Community, -Employees, -RCT Adults: http://tulane.qualtrics.com/SE/?SID=SV\_5C5tqoWuaGK4esR.
[2-4] CHOP-Community, -Employees Children: http://tulane.qualtrics.com/SE/?SID=SV\_08RuXreVqaFzV0F.
[Supplemental] Self-regulation: http://tulane.qualtrics.com/SE/?SID=SV\_beARYSuPFbCp9pH.

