The competing causal inference methods of instrumental variable and difference in difference analyses were not utilized due to their methodological weaknesses, respectively, of having varying degrees of reliable instrumental variables and having a prevalence of unobserved confounders exerting time-varying effects before and after the exposure/treatment. The above methods of doubly robust PS adjustment in multivariable regression were therefore integrated with multilevel mixed effects to provide a novel triply robust approach to causal inference. Aside from controlling for the likelihood of receiving GCCM education (via the PS) and unobserved time-invariant traits (via FE) and time variant along with intracluster correlation (via RE), this integrative method controlled via regression for age, gender, race, prior nutrition education, special diet, school year, intended specialty, and medical school. This multilevel approach has a Bernoulli conditional distribution of the response given the random effects and logistic cumulative distribution function for the success probability.

All results are reported as fully adjusted ORs. ORs rather than relative risks were calculated due to the complex data source described above and due to the rare disease assumption. Statistical significance was set at a two-tailed *p* value < 0.05. ML analysis was performed in R 3.3.2 (The R Foundation for Statistical Computing, Vienna, Austria). Statistical analysis was performed in STATA 14.2 (STATACorp, College Station, Texas, United States of America). Ethics approval was obtained through the Institutional Review Board (IRB) of Tulane University.

Version Date: 09/26/15 Version Number: 1 Page 9 of 9

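### Randomised track 4: DAC surveys follow class events in the GCCM arm and the calendar in the MNT arm, so the survey intervals are not guaranteed to match

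*Combined protocol and SAP*

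**What the plan says.** Section 1 of the protocol describes track 4 as a randomised comparison: patients "will be randomized with equal 50% chance to either taking the GCCM classes or receiving medical nutrition therapy (MNT").

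The same section gives one survey rule for tracks 2 to 4. It places the DAC surveys as follows: "first and last class for the treatment (GCCM) class group, and the beginning of the study and 2-3 months later"; the second pair of times belongs to the controls. Section 3 (Procedure) repeats the split: "DAC surveys will be used at the beginning and end of the classes for the treatment group", with study start and 2–3 months on for controls. As both sections agree, this is the intended rule and not a slip of wording.

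On the length of the intervention, Section 3 says only: "Subjects in the treatment group will receive up to 20 evidence-based classes (50 hours"). It gives no class frequency, course length or minimum attendance.

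The available text gives no survey time counted from randomisation for both arms, and no survey rule for a patient assigned to classes who never starts or stops early. (That text has no Section 11, so absence is judged without it.)

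**The concern.** Randomisation protects a comparison of DAC scores if the scores are taken at comparable times on everyone assigned. Here the timing rule itself depends on the arm. Two things could follow.

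- **Elapsed time.** If the class series does not last 2–3 months, the arms are surveyed after different intervals. Part of any difference between arms could then reflect time since baseline and not the classes.
- **Attendance.** If the last class means the last one that the patient attends, the survey date is set by behaviour after randomisation. A patient who attends no class has no defined survey. The MNT schedule has no such dependence.

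The baseline raises a smaller point. A survey at the first class comes after allocation. The documents do not say whether the MNT baseline does too.

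What is at stake is the DAC comparison in the one track where randomisation could otherwise make it clean.

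**Working it through.** The plan states no figure for course length, so there is none to reproduce. The check sets the two survey rules side by side, then asks when the intervals agree.

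**Step 1. The two rules**

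| | GCCM arm | MNT arm |
|---|---|---|
| First survey | first class / start of classes | start of study |
| Second survey | last class / end of classes | 2–3 months after that |
| What fixes the interval | number and spacing of classes | calendar |

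**Step 2. Inputs**

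- Maximum number of classes: 20 (Section 3).
- MNT interval: 2–3 months (Sections 1 and 3).
- Days between classes, d: not stated. Assumed values are 3.5 (two a week), 7 (weekly) and 14 (fortnightly).
- Days per month: 365.25 / 12 = 30.44.

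**Step 3. Interval from first to last class**

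Interval in months = (n − 1) × d / 30.44, for n classes. With n = 20:

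- two a week: 19 × 3.5 = 66.5 days; 66.5 / 30.44 = 2.2 months
- weekly: 19 × 7 = 133 days; 133 / 30.44 = 4.4 months
- fortnightly: 19 × 14 = 266 days; 266 / 30.44 = 8.7 months

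**Step 4. How many classes fit 2–3 months**

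Two months are 60.9 days and three months 91.3 days, so n − 1 must lie between 60.9 / d and 91.3 / d.

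- two a week: 17.4 to 26.1, so 19 or 20 classes (capped at 20)
- weekly: 8.7 to 13.04, so 10 to 14 classes
- fortnightly: 4.35 to 6.5, so 6 or 7 classes

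The intervals can agree, but only for certain pairs of number and spacing, and the plan fixes neither.

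**Step 5. The two readings of the last class**

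- *Scheduled series.* The second survey falls when the series ends, whoever attended. Every patient assigned to classes has a defined survey, and only the elapsed-time question of Steps 3 and 4 remains.
- *Personal attendance.* The interval varies by patient. With weekly classes and none missed before stopping, a last class that is the 4th gives 3 × 7 / 30.44 = 0.7 months, the 10th gives 2.1, the 14th 3.0 and the 20th 4.4. A patient who attends none has no interval.

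**The case against.** The case on the other side is substantial, and much of it stands.

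- **The series reading is the more natural one.** Section 3 speaks of the end of the classes for the group. On that reading no one loses a defined survey point. This stands, so the attendance problem is conditional on a reading that the wording of Section 1 permits but does not require.
- **The course may well last 2–3 months.** The control interval may even have been chosen to match it. The documents neither say so nor exclude it.
- **Withdrawal is open to both arms.** Section 4 says that subjects who feel uncomfortable "they may cease participation at any time and forgo participation". This applies equally to classes and MNT, and a patient who leaves the study would be missing under any schedule. A reader might infer differential loss from this sentence; it does not show any.
- **Both arms have a first survey.** Adjusting for it would remove part of any stable difference between patients who are surveyed and those who are not.
- **The role of DAC in track 4 is not stated.** Section 1 names DAC comparisons for tracks 1 to 3 and gives only the randomisation for track 4. This limits the importance of the point, although the surveys are still prescribed for track 4.
- **A survey at the end of an intervention is a recognised choice.** It is, and it can be kept as an extra.

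The SAP does not close the gap. Its model "controlled via regression for age, gender, race, prior nutrition education, special diet, school year, intended specialty, and medical school", which describes trainees and not track 4 patients. But the lack of any track 4 analysis in the SAP is a separate and wider issue, and it adds no weight here.

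**Conclusion.** The point holds in a limited form. In track 4 the stated survey timing depends on the arm, and nothing in the plan makes the intervals equal. Confidence is high for the differing anchors, which both sections state. The spans of 2.2, 4.4 and 8.7 months rest on assumed spacings and on all 20 classes being given.

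Three stronger conclusions are tempting, and the documents do not support them.

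- That the intervals do differ. A mismatch is possible, not shown.
- That the DAC comparison is biased by some amount, or has a given excess of false positives or a false odds ratio. The documents give no attendance or loss rate, no difference between attenders and others, and no track 4 test. No such figure can be derived.
- That the health outcomes are affected. Section 3 takes these from records over three years before and three years after exposure, worded alike for both groups, so they do not depend on DAC survey timing.

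This is a cheap improvement worth making. It is not evidence that the trial's results are unsound.

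**What to change.** For track 4, in the protocol:

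1. Take the baseline DAC survey at consent, before allocation, in both arms.
2. Set one follow-up time counted from randomisation, with one window, the same in both arms, and chosen so that the scheduled class series is normally complete. This means stating the planned course length.
3. Send the follow-up survey to everyone randomised, whatever their attendance.
4. Compare DAC scores by assigned arm, adjusting for the baseline score, and report response by arm.
5. Keep an end-of-class survey as an extra if wanted.

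The cost is mainly wording, one survey moved to the consent visit and one dated mailing. Section 12 already lists an online survey for "CHOP-Community, -Employees, -RCT Adults", so the patient need not be in class to answer. Section 10 explains contact details in terms of class reminders ("Telephone numbers are collected based on GCCM experience over the past four years that class participants find reminders about classes helpful"), so the consent form may need a line on survey contact. The downside is that patients who start classes late may be surveyed before their last class, which would slightly dilute the measured effect.
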